5.4.2. Pomalidomide

The date pomalidomide is administered and any changes in the dose will be documented in the eCRF. Date and time of all pomalidomide doses will be record in patient diaries.

5.4.3. Dexamethasone

The date dexamethasone is administered and any changes in dose will be documented in the eCRF. Date and time of all dexamethasone doses will be record in patient diaries.

5.5. Study Drug Accountability

Accountability for ACY-1215 (all centers), pomalidomide, and dexamethasone (EU only) at the study center is the responsibility of the Investigator. The Investigator will ensure that the study drug is used only in accordance with this protocol. Where allowed, the Investigator may choose to assign some of the drug accountability responsibilities to a pharmacist or other appropriate individual. Drug accountability records indicating the drug's delivery date to the study center, inventory at the study center, use by each patient, and return to Sponsor or designee (or disposal of the drug, if approved by Sponsor) will be maintained by the study center. These records will adequately document that the patients were provided the doses as specified in the protocol and should reconcile all study drug received from Acetylon. Accountability records will include dates, quantities, batch/serial numbers, expiration dates (if applicable), and patient numbers. The Sponsor or its designee will review study drug accountability at the study center on an ongoing basis during monitoring visits.

All unused and used study drug will be retained at the study center until inventoried by the monitor (or unless appropriately documented according to site procedure). All used, unused, or expired study drug will be returned to Acetylon or if authorized, disposed of at the study site and documented. All material containing study drug will be treated and disposed of as hazardous waste in accordance with governing regulations.

5.6. Prior and Concomitant Treatment

All prescription and non-prescription medications, including pharmacologic doses of vitamins, herbal medicines, or other non-traditional medicines, taken within 28 days prior to the first dose of ACY-1215 through the final visit (30 days [± 3 days] after the last dose of study drug) must be documented in the eCRF.

5.6.1. Permitted Medication

Supportive therapy for MM (e.g., erythropoietin) that is ongoing at Baseline will be permitted during the treatment phase of the study. The following medications and supportive therapies are examples of support therapies that may be used during the study:

- **Antiemetics and Antidiarrheals:** Antiemetic treatments may be used at the Investigator's discretion and in accordance with the American Society of Clinical Oncology (ASCO) guidelines after documented nausea or vomiting has occurred without medications having been used. While antiemetic choice is at the discretion of the Investigator, high dose steroids should be avoided if possible as an antiemetic therapy. Dolasetron mesylate (Anzemet) is no longer indicated for chemotherapy indications due to QT prolongation per guidance of the Food and Drug Administration (FDA). Other serotonin 5HT3 antagonists (which have been reported to prolong QT) may be used if required with caution and appropriate monitoring by the Investigator. If these agents are used

prophylactically on Cycle 1 Day 8 (when PK is performed) the time and dose must be noted on the eCRF. Antidiarrheals also may be used at the Investigator's discretion.

- Hematopoietic Growth Factors: The use of hematopoietic growth factors will not be permitted during screening in the Phase 1 or Phase 2 segments of the study or in Cycle 1 of the Phase 1b segment of the study. Hematopoietic growth factors may be used beginning with Cycle 2 of the Phase 1b segment and during all additional cycles. The use of myeloid and erythroid growth factors are to be utilized as per the recommendations of the ASCO guidelines. Treatment with myeloid growth factors is encouraged when the ANC is less than 1,000/ μ L.
- Adequate hydration is recommended for the prevention of myeloma-related kidney disease. Generally, intravenous contrast is not used in CT scanning because of the risk to the kidney. Non-steroidal anti-inflammatory drugs should be avoided.
- Bisphosphonate may be used in patients with osteolytic or osteopenic myelomatous bone disease. Commercially available bisphosphonates are to be used, preferably according to the manufacturer's recommendations, as described in the prescribing information.
- Patients with advanced stage disease and/or high tumor burden should be closely monitored, appropriate precautions should be taken, and treatment should be instituted as appropriate.
- ASA (81 or 325 mg) is to be taken daily as prophylactic anticoagulation. Patients intolerant to ASA may use low molecular weight heparin. Lovenox is recommended. Coumadin will be allowed provided the patient is fully anticoagulate, with an INR of 2 to 3.

All patients will be monitored for signs and symptoms of VTE while on pomalidomide; diagnostic algorithms are provided in Appendix 9.1.

5.6.2. Excluded Medication and Substances

The following medications and supportive therapies and procedures are prohibited during the study:

- Any anti-neoplastic treatment with activity against MM (with the exception of pomalidomide and dexamethasone).
- Radiotherapy or standard systemic therapy within 2 weeks of Baseline (C1D1). Investigational therapies or biologics within 3 weeks of Baseline. Any AEs from previous therapies must be resolved to Baseline.
- Because of the increased risk of VTE patients with MM taking pomalidomide and dexamethasone, combined oral contraceptive pills are not recommended. If a patient is currently using combined oral contraception the patient should switch to one of the effective methods described in Appendix 9.2. The risk of VTE continues for 4 to 6 weeks after discontinuing combined oral contraception. The efficacy of contraceptive steroids may be reduced during co-treatment with dexamethasone.
- Hematopoietic growth factors during screening in the Phase 1 or Phase 2 segments of the study or in Cycle 1 of the Phase 1b segments of the study.

The US pomalidomide package insert states that no formal drug interaction studies have been conducted; however pomalidomide is primarily metabolized by CYP1A2 and CYP3A and is also a substrate for P-glycoprotein (P-gp).[51]:

- Co-administration of pomalidomide with drugs that are strong inhibitors of CYP1A2, CYP3A (e.g. ketoconazole) or P-gp could increase exposure and should be avoided.
- Co-administration of pomalidomide with drugs that are strong inducers of CYP1A2, CYP3A (e.g. rifampin) or P-gp could decrease exposure and should be avoided.
- Cigarette smoking may reduce pomalidomide exposure due to CYP1A2 induction. Patients should be advised that smoking may reduce the efficacy of pomalidomide.

The Canadian pomalidomide package insert states that no formal drug interaction studies have been conducted; however, pomalidomide is a substrate of P-glycoprotein (Pg-p) and is partly metabolized by CYP1A2 and CYP3A4.[58]:

- The use of pomalidomide with concomitant strong CYP1A2 inhibitors and strong CYP3A4 inhibitors together should be avoided.
- If strong inhibitors of CYP1A2 are coadministered with pomalidomide, patients should be closely monitored for the occurrence of AEs.
- The risk of thromboembolic events may be increased with the simultaneous use of pomalidomide with erythropoietic agents, hormone replacement therapy or hormonal contraceptives.
- Cigarette smoking may reduce the exposure to pomalidomide.
- Pomalidomide may possibly impair mental and/or physical abilities required for the performance of hazardous tasks, such as driving a car or operating other complex or dangerous machinery.
- Drugs that may interact with pomalidomide include:
 - fluvoxamine, Hormonal Replacement Therapy, and
 - Hormonal Contraception (estrogens and progestins).

The EU pomalidomide package insert states that no formal drug interaction studies have been evaluated; however, pomalidomide is a substrate of Pg-p and is partly metabolized by CYP1A2 and CYP3A4/5.[59]

- Co-administration of pomalidomide with the strong CYP3A4/5 and P-gp inhibitor ketoconazole, or the strong CYP3A4/5 inducer carbamazepine, had no clinically relevant effect on exposure to pomalidomide.
- Co-administration of the strong CYP1A2 inhibitor fluvoxamine with pomalidomide in the presence of ketoconazole increased exposure to pomalidomide by 104% with a 90% CI [88%, 122%] compared to pomalidomide plus ketoconazole.
- If strong inhibitors of CYP1A2 (e.g. ciprofloxacin, enoxacin and fluvoxamine) are co-administered with pomalidomide, patients should be closely monitored for the occurrence of adverse reactions.

The dexamethasone prescribing information contains the following information regarding drug interactions [60]:

- Aminoglutethimide: Aminoglutethimide may diminish adrenal suppression by corticosteroids.
- Amphotericin B injection and potassium-depleting agents: When corticosteroids are administered concomitantly with potassium-depleting agents (e.g., amphotericin B,

diuretics), patients should be observed closely for development of hypokalemia. In addition, there have been cases reported in which concomitant use of amphotericin B and hydrocortisone was followed by cardiac enlargement and congestive heart failure.

- **Antibiotics:** Macrolide antibiotics have been reported to cause a significant decrease in corticosteroid clearance.
- **Anticholinesterases:** Concomitant use of anticholinesterase agents and corticosteroids may produce severe weakness in patients with myasthenia gravis. If possible, anticholinesterase agents should be withdrawn at least 24 hours before initiating corticosteroid therapy.
- **Anticoagulants, Oral:** Co-administration of corticosteroids and warfarin usually results in inhibition of response to warfarin, although there have been some conflicting reports. Therefore, coagulation indices should be monitored frequently to maintain the desired anticoagulant effect.
- **Antidiabetics:** Because corticosteroids may increase blood glucose concentrations, dosage adjustments of antidiabetic agents may be required.
- **Antitubercular Drugs:** Serum concentrations of isoniazid may be decreased.
- **Cholestyramine:** Cholestyramine may increase the clearance of corticosteroids.
- **Cyclosporine:** Increased activity of both cyclosporine and corticosteroids may occur when the two are used concurrently. Convulsions have been reported with this concurrent use.
- **Dexamethasone Suppression Test (DST):** False-negative results in the DST in patients being treated with indomethacin have been reported. Thus, results of the DST should be interpreted with caution in these patients.
- **Digitalis Glycosides:** Patients on digitalis glycosides may be at increased risk of arrhythmias due to hypokalemia.
- **Ephedrine:** Ephedrine may enhance the metabolic clearance of corticosteroids, resulting in decreased blood levels, and lessened physiologic activity, thus requiring an increase in corticosteroid dosage.
- **Estrogens, including Oral Contraceptives:** Estrogens may decrease the hepatic metabolism of certain corticosteroids, thereby increasing their effect.
- **Hepatic Enzyme Inducers, Inhibitors and Substrates:** Drugs which induce cytochrome P450 3A4 (CYP 3A4) enzyme activity (e.g., barbiturates, phenytoin, carbamazepine, rifampin) may enhance the metabolism of corticosteroids and require that the dosage of the corticosteroid be increased. Drugs which inhibit CYP 3A4 (e.g., ketoconazole, macrolide antibiotics such as erythromycin) have the potential to result in increased plasma concentrations of corticosteroids.
- **Dexamethasone** is a moderate inducer of CYP 3A4. Co-administration with other drugs that are metabolized by CYP 3A4 (e.g., indinavir, erythromycin) may increase their clearance, resulting in decreased plasma concentration.
- **Ketoconazole:** Ketoconazole has been reported to decrease the metabolism of certain corticosteroids by up to 60%, leading to increased risk of corticosteroid side effects. In addition, ketoconazole alone can inhibit adrenal corticosteroid synthesis and may cause adrenal insufficiency during corticosteroid withdrawal.

- Nonsteroidal Anti-Inflammatory Agents: Concomitant use of aspirin (or other nonsteroidal anti-inflammatory agents) and corticosteroids increases the risk of gastrointestinal side effects. Aspirin should be used cautiously in conjunction with corticosteroids in hypoprothrombinemia. The clearance of salicylates may be increased with concurrent use of corticosteroids. ASA (81 or 325 mg) QD is permitted for deep venous thrombosis (DVT) prophylaxis.
- Phenytoin: In post-marketing experience, there have been reports of both increases and decreases in phenytoin levels with dexamethasone co-administration, leading to alterations in seizure control.
- Skin Tests: Corticosteroids may suppress reactions to skin tests.
- Thalidomide: Co-administration with thalidomide should be employed cautiously, as toxic epidermal necrolysis has been reported with concomitant use.
- Vaccines: Patients on corticosteroid therapy may exhibit a diminished response to toxoids and live or inactivated vaccines due to inhibition of antibody response. Corticosteroids may also potentiate the replication of some organisms contained in live attenuated vaccines. Routine administration of vaccines or toxoids should be deferred until corticosteroid therapy is discontinued if possible.

6. STUDY ASSESSMENTS

6.1. Safety Measurements

6.1.1. Demographics and Medical History

A medical and surgical history will be obtained at screening for all patients. The medical history is to include demographic and background information, MM history, including date of and stage at diagnosis, and all previous treatment for MM, including radiation therapy, and response(s) to such treatment.

6.1.2. Physical Examination

A complete physical examination will be conducted for all patients at screening and at study treatment discontinuation.

6.1.3. Vital Signs

Vital signs, including weight, blood pressure (BP), heart rate, and temperature will be conducted for all patients at screening, on Day 1 of every treatment cycle, upon PD, and at study treatment discontinuation. Height will be collected at screening only.

6.1.4. Eastern Cooperative Oncology Group (ECOG) Performance Status

ECOG performance Status (Appendix 9.8) is to be documented for all patients at screening, on Day 1 of every treatment cycle, upon PD, and at study treatment discontinuation.

6.1.5. 12-Lead Electrocardiogram

Twelve-lead ECGs monitoring is to be performed at screening, pre-dose on Day 1 of every treatment cycle, Day 8 (Cycle 1 only for Phase 1B), and at study treatment discontinuation. Additional ECGs may be taken at any time point at the Investigator's discretion.

6.1.6. VTE Monitoring

Monitoring for VTE will be performed at each visit during study treatment and at study discontinuation.

6.1.7. Clinical Laboratory Tests

All serum hematology, serum chemistries, serum function tests, and urinalysis will be analyzed by local laboratories.

6.1.7.1. Hematology, Serum Chemistry and Urinalysis

Blood samples for hematology are to be collected for all patients at screening, on Days 1, 2, 8, 15, and 22 during Cycle 1, on Day 1 of every cycle beginning with Cycle 2, upon PD, and at study treatment discontinuation. In addition, complete blood count (CBC) will be conducted every 7 days for Cycle 1, every 14 days for Cycle 2, and on Day 1 of every cycle beginning with Cycle 3.

Blood samples for serum chemistry are to be collected for all patients at screening, on Day 1 of every treatment cycle, and at study treatment discontinuation. Hematology and serum chemistry results must be available and reviewed by the Investigator prior to study drug administration.

Urine for urinalysis is to be collected at screening, on Day 1 of every treatment cycle, upon PD, and at study treatment discontinuation.

The following clinical laboratory parameters are to be measured:

Hematology

- Hematocrit
- Hemoglobin
- Red blood cell count (RBC)
- INR
(for patients on coumadin)
- ANC
- Platelet count
- WBC with differential
- Reticulocyte count
- Mean corpuscular volume
- Absolute lymphocyte count (ALC)

Chemistry

- Glucose
- Calcium
- Albumin
- Total protein
- Sodium
- Potassium
- Magnesium
- Phosphorus
- Chloride
- Blood urea nitrogen (BUN)
- Uric acid
- ALP
- Creatinine
- Carbon dioxide
- Total bilirubin
- Lactate dehydrogenase (LDH)
- AST
- ALT
- Gamma-glutamyl transpeptidase (GGT)

Urinalysis

- Specific gravity
- pH
- Glucose
- Bilirubin
- Protein
- Ketones
- Microscopic examination [casts, RBCs, and WBCs]

INR will be measured at screening and on Day 1 of every treatment cycle for patients on coumadin. INR is to be between 2 to 3. If a patient's INR is outside this range, then the anticoagulant dose should be adjusted (see Section 5.6.1).

Clinical laboratory evaluations are to be repeated as necessary during treatment at a schedule determined by the Investigator, based on the patient's clinical status.

Laboratory abnormalities that are considered by the Investigator to be clinically significant for a particular patient at screening, and before study drug administration on C1D1 are to be reported as part of the patient's medical history.

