4 Vital signs will include weight, height (screening only), blood pressure (BP), temperature, and heart rate.

5 A bone marrow aspirate is to be performed at screening and a sample sent for central cytogenetic and fluorescence *in situ* hybridization (FISH) analysis (a bone marrow biopsy is needed only if the marrow is unable to be aspirated). A bone marrow biopsy/aspirate may be done as clinically indicated, at the discretion of the treating physician for assessment of disease.

6 Serum chemistry (glucose, calcium, albumin, total protein, sodium, potassium, magnesium, phosphorus, chloride, blood urea nitrogen, uric acid, alkaline phosphatase [ALP], creatinine, carbon dioxide, total bilirubin, lactate dehydrogenase [LDH], aspartate aminotransferase [AST], alanine aminotransferase [ALT], and gamma-glutamyl transpeptidase [GGT]) will be performed at screening, on Day 1 of every cycle beginning with Cycle 1 Day 1, PD, and at study treatment discontinuation.

7 Hematology will include hematocrit, hemoglobin, red blood cell (RBC) count, international normalized ratio (INR), absolute neutrophil count (ANC), absolute lymphocyte count (ALC), white blood cell (WBC) count with differential, platelet count, reticulocyte count, and mean corpuscular volume. Complete blood count (CBC) will be conducted every 7 days for Cycle 1, every 14 days for Cycle 2 (Cycle 2, Day 15), and on Cycle Day 1 of every cycle beginning with Cycle 3. INR will be measured at screening and on Day 1 of every cycle for patients on coumadin.

8 Quantitative serum immunoglobulin levels will be obtained at screening, at Day 1 of each treatment cycle, PD, and at study treatment discontinuation.

9 Serum and 24-hour urine samples for M-protein analysis (see Section 6.2.1) will be collected from all patients at screening, on Day 1 of every cycle, at PD, and at study treatment discontinuation.

10 Serum samples for SFLC analysis (see Section 6.2.2) will be collected from all patients at screening, on Day 1 of every cycle, PD, and at study treatment discontinuation.

11 IFE studies will be performed at screening, Day 1 of each treatment cycle, and to confirm CR (undetectable M-protein by protein electrophoresis in urine and serum will trigger the central laboratory to perform IFE studies in urine and serum).

12 Urinalysis will include specific gravity, pH, glucose, bilirubin, protein, ketones, and microscopic analysis (casts, RBCs, and WBCs).

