5.2.6. Dose-limiting Toxicity

Before each scheduled study drug dose administered in the clinic, the patient will be evaluated for possible toxicities that may have occurred after the previous dose(s). Toxicities are to be graded according to the NCI CTCAE, Version 4.0. If a toxicity is not classified in the CTCAE, then it should be classified according to the criteria presented in Section 6.1.8.4.

The Investigator is to assess the relationship of a toxicity to each study drug. If a toxicity is considered to be related to a particular drug(s), then the dose of the drug(s) to which the toxicity is considered related may be modified per the applicable algorithm in the following subsections. Conversely, if the toxicity is considered unrelated to a particular drug(s), then no modification of that drug(s) is required. For toxicities observed that may be attributable to pomalidomide (see Table 6) or dexamethasone (see Table 8), dose reductions should be attempted with these treatments prior to reducing the dose of ACY-1215.

The following AEs occurring during Cycle 1 that are considered to be ACY-1215-related will be considered to be DLTs:

Hematologic toxicity:

- Grade 4 neutropenia ($ANC < 500/\mu L$), lasting > 5 days, or
- Febrile neutropenia (fever $\geq 38.5^{\circ} C$ and $ANC < 1,000/\mu L$), or
- Grade 4 thrombocytopenia (platelet count $< 25,000/\mu L$), or

Grade 3 or 4 ACY-1215-related Non-hematologic toxicity:

- All other Grade 3 or Grade 4 non-hematologic toxicity with the exception of:
 - Grade 3 or 4 nausea, vomiting or diarrhea (Patients must have received optimal symptomatic treatment for Grade 3 or 4 nausea, vomiting, or diarrhea to be considered a DLT).
 - Grade 4 transaminitis (serum transaminase $> 20 \times$ upper limit of normal [ULN]) is a DLT, while Grade 3 transaminitis (serum transaminase $> 5 \times$ ULN) must be present for ≥ 7 days to be considered a DLT.
 - Other asymptomatic Grade 3 and 4 laboratory investigations, excluding cardiac function tests, may be evaluated by the SRC to determine whether dose cohorts should be expanded.
- Delay of the start of Cycle 2 by > 7 days due to ACY-1215-related AE.

Toxicity management procedures for ACY-1215 are presented in Table 4 and Table 5. No dose modifications for ACY-1215 are to be performed in Cycle 1.

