5.2.8.1. ACY-1215

Patients must remain on their assigned ACY-1215 dose in Cycle 1 during the dose escalation phase of the study, or be withdrawn from the study. If toxicity attributable to pomalidomide or dexamethasone is seen during Cycle 1, dose reductions may be made as described in Table 6 and Table 8. Patients should receive 80% of planned doses to be evaluable for SRC review.

For toxicities observed that may be attributable to pomalidomide (see Table 6) or dexamethasone (see Table 8), dose reductions should be attempted with these treatments prior to reducing the dose of ACY-1215.

After Cycle 1, patients who are unable to tolerate ACY-1215 treatment may have the dose reduction steps presented in Table 3 until a tolerable dose is achieved.

Table 3 ACY-1215 Dose Modifications

Dose level	Starting dose of ACY-1215	1 st dose reduction	2 nd dose reduction
-2	160 mg QD on Days 1-5, and 8-12	80 mg QD on Days 1-5, and 8-12	NA
-1	160 mg QD on Days 1-5, 8-12, and 15-19	80 mg QD on Days 1-5, 8-12, and 15-19	NA
1	160 mg QD on Days 1-21	80 mg QD on Days 1-21	NA
2	240 mg QD on Days 1-21	160 mg QD on Days 1-21	80 mg QD on Days 1-21
3	160 mg BID on Days 1-21	160 mg QD on Days 1-21	80 mg QD on Days 1-21

Table 4 Dose Modification Instructions for ACY-1215 for Hematologic Toxicities

Toxicity	Dose Modification
Neutropenia (1st occurrence): 
• ANC < 500/μL or febrile neutropenia (fever \geq 38.5°C and ANC < 1,000/μL)• ANC return to \geq 500/μL	Interrupt ACY-1215 treatment, follow CBC weekly. Resume ACY-1215 at one dose level lower than at the time of the first occurrence per Table 3. For the second occurrence of neutropenia (each subsequent drop of ANC < 500, interrupt and follow as above and resume at one dose level below the current dose.
Thrombocytopenia (1st occurrence): 
• Platelets < 25,000/μL• Platelets return to \geq 50,000/μL	Interrupt ACY-1215 treatment, follow CBC weekly. Resume ACY-1215 at one dose level lower than at the time of the first occurrence per Table 3. For the second occurrence of thrombocytopenia (each subsequent drop of platelets < 25,000), interrupt and follow as above. When platelet count returns to 50,000, resume at one dose level below the current dose.

Table 5: Dose Modification Instructions for ACY-1215 for Non-hematologic Toxicities

Toxicity	Dose Modification

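### Cycle 1 labs as scheduled cannot establish the Grade 3 transaminitis DLT (≥ 7 days) and only partly time the Grade 4 neutropenia DLT (> 5 days)

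*Combined protocol and SAP*

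**What the plan says.** **DLT definitions.** Section 5.2.6, like the synopsis, counts Grade 4 neutropenia (ANC below 500/µL) "lasting > 5 days, or" either of two further hematologic events, febrile neutropenia and Grade 4 thrombocytopenia, which carry no duration test. Grade 3 transaminitis has to persist for at least "7 days to be considered a DLT". Grade 4 transaminitis is a DLT whatever its duration. Events must occur in Cycle 1 and be judged ACY-1215-related.

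**Scheduled tests.** For hematology, 6.1.7.1 has "Blood samples for hematology are to be collected for all patients at screening, on Days 1, 2, 8, 15, and 22 during Cycle 1", and Table 1 footnote 7 has "Complete blood count (CBC) will be conducted every 7 days for Cycle 1". For chemistry, which includes ALT and AST, 6.1.7.1 has "Blood samples for serum chemistry are to be collected for all patients at screening, on Day 1 of every treatment cycle", and Table 1 footnote 6 says that it "will be performed at screening, on Day 1 of every cycle beginning with Cycle 1 Day 1"; progression and treatment discontinuation are the only other scheduled occasions. Results are to be reviewed before dosing, so the Cycle 1 Day 1 value is a pre-treatment one. Visit windows in Table 1 are ±2 days for Days 8, 15 and 22 and ±3 days for Day 1 of later cycles.

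**After an abnormal value.** For ANC below 500/µL, Table 4 (section 5.2.8.1) says "Interrupt ACY-1215 treatment, follow CBC weekly". Section 5.2.6 says "No dose modifications for ACY-1215 are to be performed in Cycle 1". Section 6.1.7.1 leaves repeat tests to the investigator, guided by clinical status. Section 6.1.8.4 makes clinically relevant laboratory deterioration a recordable AE and asks for onset and stop dates by grade. Section 6.1.8.5 requires related AEs to be followed until resolved, chronic or stable.

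**The concern.** A DLT defined by duration needs at least two values spaced to show that duration, or a rule for what to conclude when they are missing. For transaminases the schedule gives no on-treatment value in Cycle 1. For neutrophils it gives values a week apart against a limit of 5 days, and the Table 4 follow-up is no finer than the routine schedule. Table 4 also attaches that follow-up to interrupting ACY-1215, which Cycle 1 does not allow.

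No stated rule dates an episode between draws. An isolated low ANC dated to its own day is not a DLT; carried forward to the next weekly recovered count, it is. The neutropenia tally can therefore err in either direction, whereas a transaminase rise that is never sampled can only be missed.

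At stake is the DLT count by dose cohort that section 7.6.6 will report, chiefly at Dose Level 1, the dose taken into Phase 2. If another Phase 1b cohort were run, the limit of 1 DLT in 6 in section 5.2.5 would use the same count.

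**Working it through.** **1. The plan's own figure.** Table 11 (section 7.2) gives escalation probabilities. Under 3+3, P = (1−p)³ + 3p(1−p)²(1−p)³. At p = 0.3 this is 0.343 + 0.441 × 0.343 = 0.494, against 49% in the table; the other eight entries also reproduce. The table is correct for DLTs as counted and says nothing about whether an event can be classified.

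**2. Transaminitis.** Scheduled chemistry falls on Day 1 (pre-dose), Day 29 (Cycle 2 Day 1) and Day 57, taking nominal days and counting calendar days with both ends included.
- Two on-treatment values are 28 days apart, so no episode shorter than 4 weeks can be shown to last 7 days, and by Day 29 there is at most one such value.
- Chance of being sampled at all, onset equally likely on Days 2-28 (27 days, an assumption): a 7-day episode includes Day 29 if onset is on Days 23-28, 6/27 = 22%; a 14-day episode if onset is on Days 16-28, 13/27 = 48%.
- If at least 7 days must fall inside Cycle 1, onset is on Days 2-22 (21 days): 0/21 = 0% for a 7-day episode and 7/21 = 33% (onset Days 16-22) for a 14-day one.

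**3. Neutropenia: what one low count can mean.** Higher counts on Days 8 and 22 with a low count on Day 15 allow anything up to just under 22 − 8 = 14 days. With windows, a low Day 22 visit can be bracketed by Day 13 (15 − 2) and Day 32 (29 + 3), so just under 19 days.

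**4. Neutropenia: chance that scheduled counts show more than 5 days.** Draws are every 7 days, the episode covers d calendar days, onset is uniform over the week, and there are no extra draws. Two low counts a week apart need 8 dates inside the episode, so P = (d − 7)/7 for d = 7 to 14 and 0 below.

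| Duration (days) | Scheduled counts only | With a count on the fifth day after the first low one |
|---|---|---|
| 6 | 0% | 1/7 = 14% |
| 7 | 0% | 2/7 = 29% |
| 8 | 1/7 = 14% | 3/7 = 43% |
| 10 | 3/7 = 43% | 5/7 = 71% |
| 12 | 5/7 = 71% | 100% |

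The last column is min(1, (d − 5)/7): low on Day 8 and still low on Day 13 makes 6 calendar days. A 5-day episode gives 0, so none is wrongly called a DLT. Spreading visits evenly over their ±2-day windows (simulation) changes the scheduled-only column to about 2%, 6% and 13% for 6, 7 and 8 days, about a third for 10 and a little over half for 12.

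**5. Scale of one event.** Section 7.6.7 refers to 12 patients at the recommended dose. One reclassified event moves the observed rate by 1/12 = 8 points: for example from 1/12 = 8% (exact 95% CI 0.2-38%) to 2/12 = 17% (2-48%). The numerators are hypothetical.

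**The case against.** The strongest objection is that the matter is largely settled. The synopsis and section 3.3 fix 160 mg once daily on Days 1-21 for Phase 2, and no Phase 2 endpoint, error rate or sample size depends on Phase 1b DLT timing. That stands, and it limits the weight of the point.

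Second, the plan has safeguards beyond Table 4: investigator-scheduled repeats (6.1.7.1), mandatory AE recording and follow-up (6.1.8.4, 6.1.8.5), a separate DLT for an ACY-1215-related delay of Cycle 2 by more than 7 days (5.2.6), weekly site contact (5.2.5) and DLT confirmation by the SRC (4.8). A reader might infer that nothing but Table 4 follows a low ANC; that is not so. These provisions narrow the gap but fix no interval, and a clinically silent enzyme rise sets none of them in motion. The SRC can judge only values that exist, and for patients added to an expanded cohort section 4.8 has it review after Day 21, before the nominal Day 22 count and the first on-treatment chemistry.

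Third, section 7.6.6 already plans shift tables by cycle to the maximum grade of ANC, AST and ALT, with by-patient AE listings. Sampled candidates will therefore be visible. What is missing is a label for events whose duration is unknown and a DLT count that shows their effect.

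Fourth, section 4.8 refers to an SRC Charter that is not among the documents. It may hold a timing rule, in which case citing it would answer part of the point.

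**Conclusion.** The point holds for the schedule as written, more strongly for one DLT than for the other. Scheduled tests cannot establish Grade 3 transaminitis of at least 7 days in Cycle 1, and they leave Grade 4 transaminitis unsampled on Days 2-28. Weekly counts time Grade 4 neutropenia only in part: they catch most episodes and settle those with two low counts a week apart, but often leave episodes of about 6 to 13 days unclassified.

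The percentages assume one continuous episode, uniform onset and no discretionary repeats. They describe the bare schedule, not expected conduct.

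A reader might infer that the Phase 2 dose rests on a wrong DLT count, or that DLTs were missed. The documents do not support either: they give no number of affected patients, which may be zero, and nothing shows that duration influenced an SRC decision. Even the 2/12 in the example equals the 1-in-6 tolerance. Nor is Table 11 in error. The conclusion is limited to how firmly the Phase 1b DLT count can be read, and it merits a reporting change.

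**What to change.** **Completed cohorts, in the section 7.6.6 DLT summary.** Flag as duration undetermined each Cycle 1 ANC below 500/µL or Grade 3 ALT/AST that is possibly ACY-1215-related, is not already a DLT, and has no repeat placing it against 5 or 7 days. Report DLTs per dose level with and without these patients, alongside the shift tables already planned. State in the report that ALT/AST was not scheduled on Days 2-28. The cost is one listing and a second count among at most 30 patients, without patient contact; 7.6.6 already allows added safety analyses.

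**Any further Phase 1b Cycle 1, in 5.2.6, 6.1.7.1 and Table 1 footnotes 6 and 7.** Run ALT/AST on the Day 8, 15 and 22 draws already taken. With Day 29, every 7-day episode starting on Days 2-28 would then be sampled at least once on the nominal schedule (27/27, against 6/27 now). Repeat a Grade 3 value on the seventh calendar day. Repeat any ANC below 500/µL locally by the fifth day after the first low count, with a count on that day unless recovery is already documented. If a repeat is missed, label the event undetermined and let the SRC adjudicate; counting it automatically as a DLT would exchange an ambiguity for a known bias.

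The cost is a few extra local tests in affected patients. Time before the first low draw is still not recovered, so 6- and 7-day neutropenia would be shown in only 14% and 29%.
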